Data collection. The program manager (PM) will track recruitment and retention. A clinical assessor will conduct diagnostic interviews and questionnaire evaluations pre-, mid-, and post-intervention blind to group allocation. All pre-, mid-, and post-treatment biological measures will be conducted and analyzed by the psychophysiological and consultants, blind to group allocation.

Assessment, Data Collection, and Schedule. Instruments and other data collection tools and their description are in the [Assessment Detail](#). This strategy includes repeat measures yet minimizes response burden. Our goal is to test for effect signal. It is premature to evaluate durability and not ethical to keep subjects in a protocol where they may not be receiving effective treatment (particularly true of MIN), so we will not include a six-month follow-up period. Instead, a one-month follow-up will test symptoms and functioning and be utilized to re-connect participants to clinical services. Data collection at mid-point of treatment is warranted to replicate mid-treatment findings from our first trial. Such a finding may help determine dose effects and plan a dose-finding trial.

Outcome measures. The primary outcome is change in PTSD symptom severity from pre- to post-treatment. We hypothesize a large pre- to post-treatment effect for ACU ($d \geq 0.8$) and at least a mild treatment effect ($d \geq 0.30$) of the difference between groups (ACU vs MIN) pre- to post-treatment, with 80% probability of detecting a true group difference at $p < 0.05$ (2-sided). Main biological outcome (secondary outcome) is change from pre- to post-treatment in PPR (decreased startle by EMG eyeblink).

IV. Statistical Plan and Data Analyses

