Assumptions for Power Calculations. Assumptions are based on interpolated data since primary outcomes in our first ACU study were assessed with the PSS-SR scale and there are no PTSD studies using MIN as the sham. Furthermore, to be consistent with major PTSD research, we will use the CAPS-5 (DSM-5 version) as the primary outcome, and there are as of yet no completed clinical trials using CAPS-5. In our first study, mean pre-treatment PTSD severity score was about 62% of maximum (31.55 of 51). ACU mean decreased 50% - 31.33 (10.1) to 15.65 (13.95) and wait-list mean decreased 9.3% - 30.79 (9.54) to 27.92 (12.33) at post-treatment. We thus assume that subjects will have a baseline mean CAPS-5 score of 50 (10) and a 50% reduction of symptoms and a 38% increased variance (CAPS-5 = 25; SD = 13.8) with ACU. There are sparse data about effects of MIN, noting a 33% improvement compared to pharmacological treatment only, and a 33% less effect than ACU in the Shen study. A 2010 Cochrane systematic review of over 200 trials investigating 60 clinical conditions about general placebo effect found placebos to not have important clinical effects but may influence patient-reported outcomes in some situations (e.g., pain and nausea). The pooled relative risk calculated for placebo was 0.93 (effect of only 7%) but significant. Confidence intervals are generally wide in the placebo arm. Several clinical and methodological factors were associated with higher effects of placebo. Since our study

includes some of these factors, and since we expect MIN to have some physical effect, MIN could provide an effect as much as 33% with a wider variance. This would predict mean CAPS-5 scores (MIN) at end-treatment of 33.5 (SD 15). The conservative prediction is mean CAPS-5 reductions of 25 points with ACU and 16.5 points with MIN, an 8.5-point difference with a pooled SD of 14.4. Given our experience and data about placebo effect, we can modestly expect a 12 point between group CAPS-5 difference and a pooled SD of 15.

Treatment Effects, Power and Sample Size, Primary Hypothesis. “The efficacy of verum acupuncture (ACU) for PTSD symptom severity will be large (pre- to post-treatment Cohen’s $d \geq 0.8$), and significantly better than sham acupuncture (MIN) (between group Cohen’s $d \geq 0.30$, with 80% probability of detecting a true group difference at $p < 0.05$ (2-sided).”

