Effects. The conservative assumptions noted above will result in pre- to post-treatment Cohen’s $d = 2.07$ within group (ACU) and between group (post-treatment difference) Cohen’s $d = 0.59$, which will prove the null hypothesis false and show a large treatment effect for ACU and a moderate between-group effect size.

Sample size needed and power. The conservative assumptions would require a total of 90 patients in a two-treatment parallel-design to provide a probability of 80 percent to detect a treatment difference at a two-sided 0.05 significance level. Modest assumptions of a 12-point difference with a pooled SD of 15 requires a total of 50 patients with power of 0.80 at $\alpha < 0.05$.

This was determined using a formula for a random effects modeling (Montgomery, 1991), which may determine the necessary sample size to detect a statistically significant difference in treatment/control group means at different levels of projected effect differences.

$$n = \frac{2 * a * M^2 * \Phi^{*2}}{\Delta^2}$$

Where:

M = measure of noncentrality parameter to estimate the standard normal probability of making a type II error

n = number of replicates necessary for each treatment

a = number of treatments (a=2)

Φ^* = estimated standard deviation

Δ = difference in baseline and post treatment

Table. Examples of sample sizes necessary for significance testing at different mean and SD’s (between group: treatment (ACU) and control (MIN)) for PTSD severity (primary outcome) at power = 0.80.

Mean difference between ACU and MIN PTSD severity scores post-treatment	Φ^2	Total N Using Formula Above
8.5	12	62
	14.4	90
	15	96
	20	162
12	12	32
	15	50
	20	86

Recruitment goals are N=90, 45 per group. With a post-randomization attrition rate of 10% we will have at least 40 individuals in each group. Considering attrition, the above table indicates that for an average difference in means of 12 at end-treatment with a standard deviation of 15, a total sample size of 50 (25 in each group) would be more than adequate to report a statistical difference with 80% power. If differences in treatment group means were found to be larger than 12, we would need even fewer subjects in our treatment groups to achieve statistical significance.

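### The primary hypothesis includes an uncontrolled within-ACU criterion (d of at least 0.8) that the plan's own sham assumptions would also meet, so that half cannot support a claim of large efficacy

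*Protocol*

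**What the plan says.** The hypothesis is stated in full under *Treatment Effects, Power and Sample Size, Primary Hypothesis* in the protocol and in the SAP. It opens "The efficacy of verum acupuncture (ACU) for PTSD symptom severity will be large", defines that by a pre- to post-treatment Cohen's d of at least 0.8, and continues "and significantly better than sham acupuncture (MIN"), with a between-group d of at least 0.30. The protocol's *Outcome measures* paragraph gives the same two parts in summary.

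Under *Effects*, both documents project a within-ACU d of 2.07 and a between-group d of 0.59. They say these will "show a large treatment effect for ACU and a moderate between-group effect size". The word *large* is attached to the one-arm figure, and the randomised contrast is called moderate.

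The inputs are under *Assumptions for Power Calculations*. Baseline: "We thus assume that subjects will have a baseline mean CAPS-5 score of 50 (10"). ACU at end of treatment: "CAPS-5 = 25; SD = 13.8) with ACU". Sham: "This would predict mean CAPS-5 scores (MIN) at end-treatment of 33.5 (SD 15"). No within-arm d is printed for MIN.

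**The concern.** A pre- to post-treatment change in one arm contains everything that happens to those patients over 12 weeks: attention, expectation, natural course, continuing medication and any specific effect of needling. The sham arm exists to separate the last of these from the rest. A criterion that looks only at the ACU arm does not use it.

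If the plan expects sham to pass the same bar, passing it says nothing specific about ACU. What is at stake is the wording of the trial's conclusion. A report that follows the hypothesis could say that efficacy is large when the controlled effect is moderate or less. Read strictly as a joint requirement, the same criterion could also make the trial fail its hypothesis despite a genuine difference from sham.

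**Working it through.** **Inputs** (*Assumptions for Power Calculations*, protocol and SAP): baseline 50 (SD 10); ACU end of treatment 25 (SD 13.8), a fall of 25; MIN end of treatment 33.5 (SD 15), a fall of 16.5.

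**1. Reproduce the plan's figures.**
- Within-arm d = mean change / sqrt((SD_pre² + SD_post²)/2).
- ACU: 25 / sqrt((10² + 13.8²)/2) = 25 / 12.05 = 2.07, as stated. Dividing by the baseline SD would give 2.50 and by the post-treatment SD 1.81, so the average-variance form is the one that matches.
- Between groups: pooled SD = sqrt((13.8² + 15²)/2) = 14.4; d = 8.5 / 14.4 = 0.59, as stated.

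**2. Apply the same formula to sham.**
- MIN: 16.5 / sqrt((10² + 15²)/2) = 16.5 / 12.75 = 1.29, which exceeds 0.8.
- MIN needs a fall of only 0.8 × 12.75 = 10.2 points, about 20% of the baseline of 50, to reach the bar.

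**3. Vary the assumptions.** The 13-point row is the plan's 12-point case. It assumes that ACU still falls 25 points (25 − 12 = 13) and that the MIN post-treatment SD is 15. The documents give no pre-post correlation r, so a range is shown for the SD of change.

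| MIN fall | Average variance | Baseline SD | Post SD | SD of change, r = 0 / 0.3 / 0.5 / 0.7 |
|---|---|---|---|---|
| 16.5 | 1.29 | 1.65 | 1.10 | 0.92 / 1.08 / 1.25 / 1.54 |
| 13 | 1.02 | 1.30 | 0.87 | 0.72 / 0.85 / 0.98 / 1.21 |

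Only one cell is below 0.8: the 13-point fall with zero correlation.

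Two weaker responses would miss the bar. A 7% placebo effect (3.5 points) gives 3.5 / 12.75 = 0.27. The first study's wait-list arm gives (30.79 − 27.92) / sqrt((9.54² + 12.33²)/2) = 0.26.

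**4. Allow for sampling error.** In simulation with normal data, 40 or 45 per arm and r of 0 or 0.5, the observed MIN d (plan's formula) reached 0.8 in about 98% to 99.8% of trials with a 16.5-point fall, and in about 84% to 90% with a 13-point fall.

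**5. What the criterion does in two hypothetical trials.**
- ACU does no better than sham is assumed to do (fall of 16.5, post SD 13.8): ACU d = 16.5 / 12.05 = 1.37. The 0.8 part is met with no difference between arms.
- ACU falls 9 points and MIN does not change: ACU d = 9 / 12.05 = 0.75. The 0.8 part fails, although the 9-point difference is larger than the 8.5 points on which the trial is powered.

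**6. Basis of N.** For a difference of 8.5 and SD 14.4, total N = 4 × ((1.960 + 0.842) × 14.4 / 8.5)² = 90.1 before rounding, in line with the stated 90. The within-ACU criterion plays no part in it.

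**The case against.** The strongest reply is that the hypothesis is conjunctive. A reader who sees only its opening words might infer that the trial could declare success on the ACU change alone, with a null sham comparison. The documents do not support that. The sentence goes on to require a significant advantage over MIN, so a null comparison fails the full hypothesis whatever the within-arm d. As a joint requirement, the 0.8 part makes success harder and adds no false-positive risk. This stands.

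It is also true that the rest of the plan points to the controlled comparison. The note after *Outline of Steps of Procedures and Interventions* gives the primary goal as finding an effect relative to placebo. *General Approach* compares ACU with MIN, adjusting for baseline severity, and already plans Cohen's d within and between subjects without limiting it to ACU. The *Effects* sentence is a projection in the power section and not a formal decision rule. These facts limit the damage. They also leave the 0.8 part with no useful role.

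Two further inferences should be resisted:
- A reader might say that any control arm would clear 0.8. The 33% sham response is introduced as an upper expectation, and the 7% placebo figure and the wait-list result both fall well short. The claim is about this trial's comparator on its planning values.
- A reader might blame regression to the mean from the CAPS-5 entry cut-off of 26. At the assumed baseline of 50 (SD 10), the cut-off lies (50 − 26)/10 = 2.4 SD below the mean. Under normality, truncation there removes about 0.8% of the distribution and moves the mean by about 0.2 points, which is negligible beside a 16.5-point fall.

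**Conclusion.** The point holds in a limited form. The within-ACU criterion is not evidence of efficacy, because on the plan's own values the sham arm would meet it too: d = 1.29 in the case behind N = 90, and about 1.02 in the 12-point case. The 1.29 is derived, not printed. It rests on the stated means and SDs and on the formula that reproduces 2.07. The 1.02 also assumes that ACU still falls 25 points and that the MIN post-treatment SD is 15.

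The consequence is mislabelling, not a false positive. The joint wording protects the overall test, but it allows efficacy to be called large when the controlled effect expected is 0.59, and it could reject a trial that shows a real difference from sham. The randomised comparison and its power calculation are unaffected by this point.

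**What to change.** Amend the protocol (*Outcome measures*; *Treatment Effects, Power and Sample Size, Primary Hypothesis*; *Effects*) and the matching SAP text as follows:

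- Make the ACU-versus-MIN difference in CAPS-5 change from baseline to end of treatment the sole primary hypothesis. This agrees with the placebo-controlled goal stated elsewhere in the protocol and with the basis for N = 90.
- Remove the within-ACU d of at least 0.8 as a criterion for efficacy.
- Base any statement about the size of the treatment effect on the between-group d, and reword the *Effects* sentence accordingly.
- Report within-arm d for both ACU and MIN, side by side, as descriptive.

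The cost is wording only. Within-arm d is already to be calculated, and sample size, alpha, allocation and assessments do not change. The sponsor gives up a claim that a one-arm change cannot support.

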This was determined using a formula for a random effects modeling (Montgomery, 1991), which may determine the necessary sample size to detect a statistically significant difference in treatment/control group means at different levels of projected effect differences.

$$n = \frac{2 * a * M^2 * \Phi^{*2}}{\Delta^2}$$

Where:

M = measure of noncentrality parameter to estimate the standard normal probability of making a type II error

n = number of replicates necessary for each treatment

a = number of treatments (a=2)

Φ^* = estimated standard deviation

Δ = difference in baseline and post treatment

Table. Examples of sample sizes necessary for significance testing at different mean and SD’s (between group: treatment (ACU) and control (MIN)) for PTSD severity (primary outcome) at power = 0.80.

Mean difference between ACU and MIN PTSD severity scores post-treatment	Φ^2	Total N Using Formula Above
8.5	12	62
	14.4	90
	15	96
	20	162
12	12	32
	15	50
	20	86

Recruitment goals are N=90, 45 per group. With a post-randomization attrition rate of 10% we will have at least 40 individuals in each group. Considering attrition, the above table indicates that for an average difference in means of 12 at end-treatment with a standard deviation of 15, a total sample size of 50 (25 in each group) would

be more than adequate to report a statistical difference with 80% power. If differences in treatment group means were found to be larger than 12, we would need even fewer subjects in our treatment groups to achieve statistical significance.

PPR Data Recording and Reduction. A description of the procedure/data is in [Appendix 4](#). Data reduction and analyses will follow current established protocols in our lab (Norrholm et al, 2011a). Data will be collected with the BioSemi recording software (BioSemi B.V, Amsterdam, Netherlands) and the resulting data will be exported to Mindware software (Mindware Technologies LTD, Gahanna, OH) for data reduction and generation of analyzable variables.

Startle data reduction for analyses. The raw EMG signal will be recorded at a rate of 1000 Hz throughout the experimental session using a 28 Hz high pass and 500 Hz low pass filter (as recommended by guidelines for human eyeblink startle in Blumenthal et al., 2005; *Psychophysiology*, 42:1-15). Raw signals will be stored and exported for analysis in microvolt (μV) values.

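### N = 90 gives 80% power for the conservative case only with no dropout; at the plan's own 40 per arm it is about 74%, and the table entry 162 should be 174

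*Protocol*

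**What the plan says.** The power assumptions in the protocol call one scenario conservative: "an 8.5-point difference with a pooled SD of 14.4". Under the heading on sample size and power, it continues: "The conservative assumptions would require a total of 90 patients in a two-treatment parallel-design to provide a probability of 80 percent". The test is two-sided at the 5% level. A second, more favourable scenario follows: "Modest assumptions of a 12-point difference with a pooled SD of 15 requires a total of 50 patients".

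Below the table, the recruitment goal is set at 90, 45 per group. The next sentence reads: "With a post-randomization attrition rate of 10% we will have at least 40 individuals in each group". The text then takes attrition into account, but only by comparing the remaining sample with the 50 patients needed for 12 points and SD 15. No power is given for 8.5 points and SD 14.4 at 40 per arm.

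The Recruitment paragraph of the protocol says that participants who withdraw after starting treatment are not replaced, that 40 per group would remain for a completers' analysis, and that data from those who withdraw are kept for intent-to-treat analyses.

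The table, under "Total N Using Formula Above", lists 162 for a difference of 8.5 and an SD of 20. The SAP repeats the power text and the table.

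**The concern.** The number required under the conservative case and the number to be recruited are both 90, with an expected 10% loss in between that the calculation does not allow for. A reader who sees 80% power, a goal of 90 and a reassurance about attrition would conclude that the conservative case survives dropout. The reassurance covers only the other case.

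This matters because the inputs are uncertain. The plan itself says that they are interpolated from another scale, that no CAPS-5 trial has been completed, and that no PTSD study has used this sham. The conservative case is therefore the one a reader would rely on when interpreting a null result.

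The 162 entry is a smaller matter, but that row shows what happens if the SD is larger than hoped, and it understates the answer.

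**Working it through.** **Inputs** (protocol, power assumptions and sample size section): two-sided alpha 0.05; power 80%; difference 8.5, SD 14.4, so d = 8.5/14.4 = 0.590; 1:1 allocation; 90 randomised; 10% attrition, 45 × 0.9 = 40.5, stated as at least 40 per group.

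**Step 1. Reproduce the 90.** The printed formula is 2·a·M²·SD²/Δ². With a = 2 and M = 1.96 + 0.8416 = 2.8016 (M² = 7.849), it gives the total N:

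4 × 7.849 × 14.4² / 8.5² = 31.396 × 207.36 / 72.25 = 90.1

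So 90 reproduces, with no allowance for loss. Power at 45 per arm is 79.95% by the normal approximation and 79.1% by the noncentral t. The t-test needs 94 in total for 80%.

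**Step 2. Power at 40 per arm.**

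- Normal approximation: 0.590 × √(40/2) = 2.640; Φ(2.640 − 1.960) = 75.2%.
- Noncentral t, 78 df: 74.1%.
- With 40.5 per arm: 75.7% and 74.7%.

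Compared by the same method, the loss is about 5 percentage points.

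**Step 3. Difference detectable with 80% power at 40 per arm.** By t-test d = 0.634, and 0.634 × 14.4 = 9.1 points.

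**Step 4. What baseline adjustment could recover.** The documents give no correlation between baseline and post-treatment scores, so these values are assumptions. Adjustment multiplies the SD by √(1 − r²). The r that restores 80% at 40 per arm is √(1 − (0.590/0.634)²) = 0.37.

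| Assumed r | Power at 40 per arm, t-test | Normal approximation |
|---|---|---|
| 0 | 74.1% | 75.2% |
| 0.3 | 78.0% | 79.0% |
| 0.37 | 80.1% | 81.1% |
| 0.5 | 85.3% | 86.2% |

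**Step 5. The table.** The same formula applied to every row:

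| Difference | SD | Stated total | Formula | t-test total |
|---|---|---|---|---|
| 8.5 | 12 | 62 | 62.6 | 66 |
| 8.5 | 14.4 | 90 | 90.1 | 94 |
| 8.5 | 15 | 96 | 97.8 | 100 |
| 8.5 | 20 | **162** | **173.8** | **176** |
| 12 | 12 | 32 | 31.4 | 34 |
| 12 | 15 | 50 | 49.1 | 52 |
| 12 | 20 | 86 | 87.2 | 90 |

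Six rows lie within 2 of the formula and within 4 of the t-test. The SD 20 row at 8.5 points is 12 low, about 7%. A one-sided test would give 138, so that does not explain it either.

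The table's own scaling also contradicts it:

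- 62 × (20/12)² = 172
- 90 × (20/14.4)² = 174
- 96 × (20/15)² = 171
- 86 × (12/8.5)² = 171

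At N = 162 the power is 76.7% by t-test (77.2% normal).

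**The case against.** The strongest reply is that 40 per arm is the completer set, not the primary analysis set. The primary analysis is an intent-to-treat mixed model of CAPS at mid-treatment, end of treatment and one month, controlling for baseline. It keeps the earlier data of those who withdraw. On that view, 74% is the power of an unadjusted completers' t-test that nobody plans to report as primary, and a modest correlation removes the shortfall.

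Much of this stands. A shortfall in the planned model has not been shown, and Step 4 indicates how little correlation would be needed. But the sample size section itself counts 40 per group, its formula takes no credit for adjustment or repeated measures, and no correlation is stated anywhere. The power claim has to be judged on the calculation offered for it.

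It is also fair that the 12-point case is named openly and has about 94% power at 40 per arm, and that nowhere does the plan explicitly claim 80% after attrition for 8.5 points. The gap is a missing figure for the case that fixed N.

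Setting a t-test 74% against a normal-approximation 80% does mix methods, but this shifts results by about one point. Finally, 162 does not drive the choice of 90; it is a table correction only.

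**Conclusion.** Both parts hold. For 8.5 points and SD 14.4, the stated 80% applies to 90 evaluable patients. At the 40 per arm that the plan expects, power is about 74% to 75% for an unadjusted end-of-treatment comparison in which those who drop out contribute nothing. If the baseline-adjusted model reaches a correlation of about 0.37 or more, 80% is restored; the documents neither state nor support a value. Under 12 points and SD 15 the trial remains well powered after dropout.

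The entry 162 is wrong on the plan's own formula and should be 174. It has no effect on the planned size.

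The shortfall is modest and does not threaten the design, but the power statement should be corrected.

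**What to change.** Keep N = 90 and restate the power in the protocol and in the SAP copy of the same text: with about 40 evaluable per arm, an unadjusted comparison has about 74% power for 8.5 points (SD 14.4) and 80% power for 9.1 points. If power is meant to rest on the baseline-adjusted mixed model, say so, and give the assumed baseline-to-post correlation with its justification.

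Change 162 to 174 in both tables. While the table is open, correct two labels: the column headed as a squared quantity holds SDs, and the formula's n is defined per treatment although its result is used as the total. The restated text should also be reconciled with the primary hypothesis, which ties 80% probability to a between-group d of at least 0.30; a true d of 0.30 has about 26% power at 40 per arm.

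The cost is revised wording and figures in two documents. No patients are added, and the stated power becomes less favourable. If the sponsor would rather keep 80% unadjusted after 10% loss, the number randomised would be about 100 (90/0.9) by the plan's formula, or 105 (94/0.9, 106 for equal arms) by t-test.
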